### **6.4.2 Treatment Effect Durability**

To assess durability of treatment effects, subjects will be analyzed based on their double-blind treatment assignment and subsequent open-label treatment. Slope analyses using mixed models for repeated measures will be performed to evaluate trajectory of change in key efficacy parameters over the entire study period.

## 6.5 Subgroup Analyses

To assess the consistency of treatment effects across the subgroup levels, and to examine baseline biomarkers for their potential value to predict treatment response, exploratory subgroup analyses will be conducted for safety, tolerability, pharmacokinetics, and efficacy for the variables below.

The following subgroups will be assessed using the primary endpoint and primary endpoint related to clinical assessments, secondary endpoints, and exploratory endpoints.

- DMD disease stage (Early LVEF>45%, Late LVEF 35%-45%)
- Ambulation status (ambulatory vs non-ambulatory)
- Background therapy (none, steroids, ASO, steroids + ASO)

For each subgroup analysis, results will be presented as stratified analyses with descriptive statistics and treatment effect estimates within each subgroup level. Forest plots will be used to display treatment effects across subgroup levels for key endpoints. No formal statistical testing for interaction between subgroup and treatment will be performed due to limited sample sizes within subgroups, but the consistency of treatment effects across subgroup levels will be evaluated qualitatively. These analyses are considered exploratory and intended to identify potential patterns that may inform future research rather than to draw definitive conclusions about differential treatment effects.

Missing data in each factor, which will be limited if any, will not be included (as a separate group) in subgroup analyses. This does not apply to the PSM analysis.

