5.4 Dose Rationale

Oral ifetroban doses \geq 100 mg have been shown to inhibit TPr induced platelet aggregation, with corresponding plasma C_{max} levels of > 500 ng/mL. The bioavailability of oral ifetroban capsules has previously been found to be $\approx 42\%$. Our multi-dose safety studies have found oral ifetroban at up to 500 mg daily to be safe and well tolerated however these studies did not include children. For this reason, this study aims to compare two dose ranges of oral ifetroban (a low dose and high dose based on weight) to placebo for at least twelve months. A placebo treatment arm is included to help provide data on the natural history of the disease.

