7.2 Drugs and Dosages

Oral ifetroban is available as the sodium salt of the free acid and is for investigational use only. The drug is supplied as a capsule dosage form (size # 1, white opaque) for oral administration. Ifetroban capsules are formulated as a dry powder blend and filled into hard gelatin capsules. The formulation consists of ifetroban, mannitol, microcrystalline cellulose, crospovidone, magnesium oxide, colloidal silicon dioxide, and magnesium stearate. Capsules are filled into high density polyethylene bottles and sealed with screw-cap closures. Capsules are only available at one strength of the sodium salt, i.e., 52.5 mg corresponding to a free-acid dose of 50 mg.

Matching placebo capsules are formulated as a dry powder blend filled into capsules. The formulation consists of microcrystalline cellulose, crospovidone, colloidal silicon dioxide, and magnesium stearate. Capsules are filled into high density polyethylene bottles and sealed with screw-cap closures.

The bottles of oral ifetroban or placebo will contain the following information on the label:

PLACEBO OR IFETROBAN CAPSULES 50 MG

Quantity: 75 Capsules

Instruction: Take capsules by mouth as directed.

Store at controlled room temperature, 20°C – 25°C (68°F – 77°F)

Caution: New Drug-Limited by Federal law to investigational use

Cumberland Pharmaceuticals Inc.

Additionally, each individual bottle will be labelled with a unique numeric code that identifies the contents to the unblinded sponsor representative. Subjects will be randomized to low-dose ifetroban, high-dose ifetroban or placebo.

Low Dose: < 35 kg: 50 mg, ≥ 35 kg: 100 mg/day

High Dose: < 35 kg: 150 mg, ≥ 35 kg: 300 mg/day

Table 7-1 Ifetroban Dose Levels & Sub-Groups

DMD Sub-Group	Low Dose	High Dose	Placebo
Early Stage (LVEF > 45%)	8 subjects	8 subjects	8 subjects

DMD Sub-Group	Low Dose	High Dose	Placebo
Advance Stage (current/historical LVEF 35-45%)	8 subjects	8 subjects	8 subjects

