11.3 Subgroup analysis

To assess the consistency of treatment effects across the subgroup levels, and to examine baseline biomarkers for their potential value to predict treatment response, exploratory subgroup analyses will be conducted for safety, tolerability, pharmacokinetics and efficacy with respect to age group, race, DMD disease stage, baseline LVEF, muscle strain and other CMR parameters, baseline PFT, PedsQL, GI module & NMM values and selected biomarkers prior to the study. The details will be provided in the Statistical Analysis Plan.

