#### **4.4.4 Multiple Comparisons/Multiplicity**

Multiplicity and multiple comparisons do not apply to these secondary and exploratory objectives. No adjustments will be made for multiple comparisons or multiplicity. Changes to Protocol Specified Analysis

There are no changes to the protocol specified analyses.

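### SAP 6.5 replaces the subgroup factors named in Protocol 11.3 without declaring it; the loss that matters most is age group, because no safety summary by age is then planned

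*SAP*

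**What the plan says.** Protocol 11.3 states that "exploratory subgroup analyses will be conducted for safety, tolerability, pharmacokinetics and efficacy with respect to age group, race, DMD disease stage, baseline LVEF". It continues with strain and other CMR parameters, baseline lung function, the PedsQL instruments and selected biomarkers. It closes: "The details will be provided in the Statistical Analysis Plan".

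SAP 6.5 opens almost identically but narrows the scope: "exploratory subgroup analyses will be conducted for safety, tolerability, pharmacokinetics, and efficacy for the variables below". The variables below are three: disease stage, ambulation status and background therapy. The next sentence, "The following subgroups will be assessed using the primary endpoint and primary endpoint related to clinical assessments", confirms that safety is covered, since SAP 3.3.1 makes safety the primary endpoint. SAP section 7 then has safety data summarised by subgroup, among other splits, and 6.5 is the section that lists the subgroups.

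On departures from the protocol, SAP 4.4.4 says "There are no changes to the protocol specified analyses", and SAP section 8, reserved for such changes, is marked as not applicable.

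On children, Protocol 5.4 reports that multi-dose studies at up to 500 mg daily found oral ifetroban "to be safe and well tolerated however these studies did not include children". It gives this as the reason for comparing two dose ranges with placebo. Protocol 7.3.1 admits males from age 7 and sets no upper limit.

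**The concern.** The protocol fixes the factors and leaves their details to the SAP. The SAP changes the factors and says that nothing has changed. A reader who relies on SAP 4.4.4 or section 8 would believe that safety by age is still planned.

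Age is the factor with the most at stake. The primary objective is safety, the protocol itself identifies children as absent from the earlier multi-dose safety studies, and each arm may contain both boys and adults. If adverse events are tabulated only by arm, stage, ambulation and background therapy, a problem concentrated in younger subjects could be diluted. A clean arm-level table might also be taken as reassurance about children that it does not give.

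**Working it through.** This is mainly a comparison of texts. The plan gives no figure to reproduce.

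**Step 1. The two factor lists.**

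| Factor | Protocol 11.3 | SAP 6.5 |
|---|---|---|
| Age group | yes | no |
| Race | yes | no |
| Disease stage | yes | yes |
| Baseline LVEF | yes | no (only through stage, which is defined by LVEF) |
| Strain and other CMR parameters | yes | no |
| Baseline lung function | yes | no |
| PedsQL, GI and NMM | yes | no |
| Selected biomarkers | yes | no |
| Ambulation status | no | yes |
| Background therapy | no | yes |

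One protocol factor is kept and two new ones are added. SAP 6.5 still gives the study of baseline biomarkers as an aim, yet lists none. This suggests that the list was shortened without the introduction being revisited.

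**Step 2. Does age return elsewhere in the SAP?** Age appears as a demographic variable (5.2), in the PedsQL cohorts (6.2.4), in the QMT index (6.3.1 and 9.1.2) and as a propensity-score covariate (4.5.1 and 14.3.4). None of these splits adverse events, laboratory tests, ECG or vital signs by age. Sections 7.1 and 7.2 do not mention age.

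**Step 3. Is the change declared?** No: see SAP 4.4.4 and section 8.

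**Step 4. Could an age table be informative?** SAP 3.5 plans about 48 subjects in three equal groups: 48/3 = 16 per arm, so 32 on ifetroban. The documents do not give the share under 18, so a range is assumed. For n children:

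- chance of at least one case of an event with true rate 10% = 1 - 0.9^n
- exact two-sided 95% upper limit after zero events = 1 - 0.025^(1/n)

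| Assumed share under 18 | n, one arm | Chance of a case | Upper limit | n, both ifetroban arms | Chance of a case | Upper limit |
|---|---|---|---|---|---|---|
| 25% | 4 | 34% | 60% | 8 | 57% | 37% |
| 50% | 8 | 57% | 37% | 16 | 81% | 21% |
| 75% | 12 | 72% | 26% | 24 | 92% | 14% |

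For a whole arm of 16 the zero-event limit is 1 - 0.025^(1/16) = 21%. Reading that 21% as a statement about children would understate the uncertainty: with 4 to 12 children in the arm the limit is 60% to 26%.

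**Step 5. Dilution, purely as an illustration.** Suppose a harm has a rate of 40% in children and 5% in adults; neither rate comes from the documents. With a quarter of the arm children, the arm shows 0.25 × 40% + 0.75 × 5% = 13.75%. With half, it shows 0.5 × 40% + 0.5 × 5% = 22.5%.

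**The case against.** **The analyses are exploratory and the protocol defers to the SAP.** True, and the protocol gives no age cut, so choosing one is properly the SAP's job. But the protocol names the factors itself. Dropping one is a change, and it should be declared.

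**The cells are too small.** This has weight. Three age bands across every safety table would average 16/3, or about five subjects per arm and band, which is more than the trial can usefully support. It does not rule out two bands. SAP 6.5 already accepts four background-therapy levels, averaging 16/4 = 4 per arm, and runs no interaction tests.

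**The information will exist anyway.** Adverse events, laboratory results and demographics are listed by subject (SAP 5.2, 7.1 and 7.2), so with about 48 subjects each child's events can be traced. Protocol 13.1 also provides frequent unblinded safety review and monitoring of exposure against safety. These points stand as protection during the trial and as raw material, but neither is a planned summary with rates by age.

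**Dilution may be slight.** Also fair: if most subjects are under 18, the arm total is close to the paediatric result. The documents do not say.

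**Stronger readings that the documents do not support.** A reader might infer that the trial was run because children had not been studied. Protocol 5.3 rests the trial on preclinical cardiac data; 5.4 uses the absence of children only to explain the dose comparison with placebo. A reader might also infer that safety in children will go unreported. The listings contradict that, and the table shells are a separate document not available here. What can be said is that the SAP text gives no basis for an age-split safety summary.

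**Conclusion.** The undeclared mismatch is established from the text. SAP 6.5 keeps one protocol factor, adds two and drops the rest, while SAP 4.4.4 and section 8 say otherwise. For age the omission has practical weight, because it removes the only planned safety summary for the group that the protocol says was absent from earlier multi-dose studies.

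The size is moderate. No sample-size or power figure depends on it, and the primary endpoint is still reported by arm. An age table would be imprecise: under the assumed shares of 25% to 75%, zero events among ifetroban-treated children leaves a two-sided 95% upper limit of 37% to 14%. Those limits depend on the assumed age mix. The dilution percentages depend on invented event rates as well and are not estimates for this trial.

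A reader might extend the point to a missing split by body weight, since dosing depends on weight. Protocol 11.3 does not name weight, so its absence is not a departure from the protocol and forms no part of this conclusion.

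**What to change.** 1. In SAP 6.5, restore age group with a prespecified cut. The documents' own consent boundary, 7-17 versus 18 and older, is a natural choice: it owes nothing to the accumulated data, which matters because SAP 4.3 describes the interim analysis as already done.
2. In SAP section 7, apply it descriptively, at least to the TEAE and SAE summaries by treatment group, with n, percentage and exact two-sided 95% confidence interval.
3. Correct SAP 4.4.4 and section 8 so that they list the other dropped factors (race, baseline LVEF, CMR parameters, lung function, PedsQL and biomarkers) and the added ones (ambulation and background therapy), each with a reason. If the sponsor decides to leave age out after all, that too belongs there with its reason.

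The cost is SAP wording and repeat runs of planned tables on data already collected. The drawback is small cells, so the tables should carry no tests and be labelled as descriptive.

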## 7 SAFETY ANALYSIS

Evaluations of safety will be performed on the Safety Analysis Set. The incidence of AEs, laboratory safety test variables, abnormal ECG findings, Vital signs (including weight), Physical examination along with change from baseline will be summarized by visit, treatment group, subgroup and overall.

Study Day 1 for all safety analyses is defined as the date of the first dose of study drug.

### 7.1 Adverse Events

The AE verbatim descriptions (investigator terms from the CRF) will be classified into standardized medical terminology using the MedDRA. Adverse events will be coded to the MedDRA (Version 27.0 or higher) LLT closest to the verbatim term. The linked MedDRA PT and primary SOC will also be captured in the database.

A treatment-emergent adverse event (TEAE) will be defined as an AE that starts during or after dosing or starts prior to dosing and increases in severity after dosing.

A treatment related AE will be defined as an AE with a relationship of possible, probable, unlikely, or unrelated to the study treatment, as determined by the investigator.

All AEs will be listed. In addition to the data recorded in the database, the listings will include derived onset time and duration. Onset time will be calculated from the time of dosing for TEAEs only.

The frequency of subjects with TEAEs/serious adverse events (SAEs) and the number of TEAEs/SAEs will be summarized for the following categories:

- TEAEs/SAEs (overall, serious, leading to discontinuation, and leading to death)
- TEAEs by severity
- Treatment-related AEs/SAEs (overall, serious, leading to discontinuation, and leading to death)
- Treatment-related AEs by severity
- TEAEs leading to discontinuation of study drug.
- TEAEs by SOC and PT.
- TEAEs by PT

A subject will be counted only once within a SOC and PT, even if the subject experienced more than one TEAE within a specific SOC and PT. The number (percentage) of subjects with TEAEs will also be summarized by maximum severity (mild, moderate, or severe). The number (percentage) of subjects with TEAEs will also be summarized by relationship to study drug (related and not related).

For the AE data the following rules will apply:

- For the derivation of treatment-emergent status (applicable to all AEs): If the start date/time of an AE is incomplete or missing, an AE will be assumed to be a TEAE, unless the incomplete start date/time or the end date/time indicates an AE started after dosing.
- For the derivation of treatment-related status (applicable to TEAEs only): If the study treatment relationship for a TEAE is missing, a TEAE will be assumed to be a treatment-related TEAE.

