6.4 Primary Endpoint

Safety and tolerability (baseline to 12 months): percentage of subjects with one or more treatment emergent adverse events (TEAE) .

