10.1.2 Adverse Event Assessment Definitions

Severity

The maximum severity of an adverse event is assessed by the investigator using the following definitions:

- Mild: Transient symptoms, no interference with the subject's daily activities.
- Moderate: Marked symptoms, moderate interference with the subject's daily activities.
- Severe: Considerable interference with the subject's daily activities, unacceptable.

Relationship

The causal relationship between an adverse event and the trial product is assessed by the investigator using the following definitions:

- Probable: Good reasons and sufficient documentation to assume a causal relationship.
- Possible: A causal relationship is conceivable and cannot be dismissed

- **Unlikely:** The event is most likely related to an etiology other than the trial product.

An adverse event is considered causally related to the use of the trial product when the relationship assessment is probable or possible. Events assessed as unlikely related to the use of trial product will generally be considered as having no relationship to treatment.

Outcome

The outcome of an adverse event is assessed by the investigator using the following definitions:

- **Recovered:** Fully recovered, or by medical or surgical treatment the condition has returned to the level observed at the first trial-related activity.
- **Recovering:** The condition is improving and the subject is expected to recover from the event. This term should only be used when the subject has completed the trial.
- **Recovered with sequelae:** As a result of the AE the subject suffered persistent and significant disability/incapacity (e.g. became blind, deaf, paralyzed). Any AE recovered with sequelae should be classified as SAE.
- **Not recovered:** The subject's condition has not improved and the symptoms are unchanged
- **Fatal**
- **Unknown:** The subject's condition is unknown. This term should only be used when no other definition is possible (e.g. the subject is lost to follow-up).

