10.2 Collection, Recording and Reporting of Adverse Events

For this study, all events meeting the definition of an adverse event must be collected and reported from the first trial-related activity after the subject signs the informed consent and until end of post-treatment period.

The investigator should record the diagnosis, if available. If no diagnosis is available the investigator should record each sign and symptom as individual adverse events.

The investigator must report initial information on all serious adverse events within 24 hours of obtaining knowledge of the event. Furthermore, the investigator must complete the SAE forms within five days of obtaining knowledge of the SAE. The monitor must be informed accordingly.

The investigator must inform the IRB in accordance with local requirements in force and the ICH guidelines for GCP and the Food and Drug Administration (FDA) Title 21 Code of Federal Regulations, Part 312.32.

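### SAP 7.1 reverses the partial-date rule for treatment-emergent AEs, which feeds the primary endpoint, and counts 'unlikely' and 'unrelated' events as treatment-related

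*SAP*

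**What the plan says.** **TEAE status.** SAP 7.1 says a TEAE is "defined as an AE that starts during or after dosing or starts prior to dosing and increases in severity after dosing". Protocol 11.2.1 likewise opens the treatment-emergent period at the first administration. For incomplete dates, SAP 7.1 sets a default: "If the start date/time of an AE is incomplete or missing, an AE will be assumed to be a TEAE". It then adds an exception: "unless the incomplete start date/time or the end date/time indicates an AE started after dosing".

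SAP Appendix 2 (14.2) also covers AE start dates. A partial date in a month or year before the first dose becomes the last day of that month or year. One in a later month or year becomes its first day. One in the dosing month or year becomes the first dosing date. With the year missing, nothing is imputed. The SAP does not say whether 7.1 or Appendix 2 governs.

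**Relatedness.** SAP 7.1 states: "A treatment related AE will be defined as an AE with a relationship of possible, probable, unlikely, or unrelated to the study treatment". Protocol 10.1.2 states: "An adverse event is considered causally related to the use of the trial product when the relationship assessment is probable or possible". It adds that events judged unlikely are generally taken as having no relationship to treatment. SAP 7.1 itself plans a two-level summary of related and not-related TEAEs, and counts a TEAE with a missing relationship as related.

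Neither departure is declared. SAP 4.4.4 says there are no changes to the protocol-specified analyses, and SAP 8 is marked not applicable.

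**The concern.** Safety is the primary objective, and the percentage of subjects with at least one TEAE is the primary endpoint (Protocol 6.4; SAP 3.3.1). The rule that decides whether an event is a TEAE therefore has to point the right way.

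Pre-dose events can be in the database. Protocol 10.2 collects AEs "from the first trial-related activity after the subject signs the informed consent", and screening lasts up to 12 weeks. A screening-period event with a partial date would be counted as a TEAE even if its month or year shows that it began before the first dose. An event whose month or year shows onset after dosing would lose the assumption that it is a TEAE.

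The relatedness definition does not touch the primary endpoint. It does govern the related-AE and related-SAE summaries, including those for discontinuation and death. If every category is related, those summaries cannot separate events attributed to the drug from the rest.

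**Working it through.** The plan states no figure that depends on these rules, so the check is one of logic, with a small calculation for scale.

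**1. Partial dates.** Assume, for illustration only, a first dose on 15 May 2024 and an event that does not worsen after dosing. Three rules are applied to partial start dates: SAP 7.1 as written; SAP 7.1 with *before* in place of *after* in the exception; and Appendix 2 imputation followed by the SAP's TEAE definition.

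| Known part of start date | What it shows | 7.1 as written | 7.1 with *before* | Appendix 2, then definition |
|---|---|---|---|---|
| April 2024 | before dose | TEAE | not TEAE | 30 Apr 2024, not TEAE |
| May 2024 | undetermined | TEAE | TEAE | 15 May 2024, TEAE |
| June 2024 | after dose | assumption removed | TEAE | 1 Jun 2024, TEAE |
| 2023 | before dose | TEAE | not TEAE | 31 Dec 2023, not TEAE |
| 2024 | undetermined | TEAE | TEAE | 15 May 2024, TEAE |
| 2025 | after dose | assumption removed | TEAE | 1 Jan 2025, TEAE |
| nothing | undetermined | TEAE | TEAE | no imputation |

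As written, 7.1 gives the wrong answer in all 4 cases where the partial date is informative, and a sensible one only in the 3 where it is not. With *before*, it agrees with Appendix 2 in all 6 cases where Appendix 2 gives a date.

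The wording of the exception also suggests a slip. It allows the end date to serve as evidence. An end date after dosing cannot by itself show that onset was after dosing, but an end date before the first dose does show that onset was before it. Citing the end date makes sense only if *before* was intended.

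**2. Scale for the primary endpoint.** Change in an arm's percentage per subject whose TEAE status changes = 100 / n.

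- n = 16 (48 subjects in three arms; SAP 3.5): 100/16 = 6.25 points.
- n = 18 (54 recruited, SAP 3.4; 54/3): 100/18 = 5.6 points.
- n = 20 (60 recruited, Protocol 11.1; 60/3): 100/20 = 5.0 points.

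The last two apply if all recruited subjects are dosed, since the endpoint is analysed in the Safety Population.

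**3. Relatedness.**

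| Investigator's assessment | SAP 7.1 | Protocol 10.1.2 |
|---|---|---|
| Probable | related | related |
| Possible | related | related |
| Unlikely | related | not related |
| Unrelated | related | not a listed category |
| Missing | related (by rule) | not addressed |

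Under SAP 7.1 all 5 outcomes are related, so the not-related row is always 0. The special rule for a missing relationship would have no purpose if every assessed category were already related.

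**The case against.** The strongest reply accepts that both sentences are wrong but disputes their effect.

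- *The general definition still applies.* The exception lifts an assumption; it does not declare a post-dose event non-emergent. A programmer could restore such an event through the TEAE definition or Appendix 2. This is possible, but the ordinary reading of the sentence removes the event, and an analysis plan should not depend on the programmer overriding it. Nothing in the 7.1 rule prevents pre-dose events from being kept.
- *Appendix 2 repairs most cases.* If imputation runs first, 7.1 is left mainly with starts whose year is missing, where the default is reasonable unless an end date shows pre-dose onset. This would hold if the SAP gave Appendix 2 precedence. It does not, so two rules give opposite answers.
- *The effect may be small.* Only events with incomplete starts are affected, and a subject's status on the primary endpoint changes only if no other correctly classified TEAE exists. Over 12 months of AE recording, many misclassified events may change nothing. This stands. Protocol 10.1.1 also keeps pre-existing conditions found at screening out of the AE record unless they worsen.
- *Relationship data survive elsewhere.* Protocol 11.8.4 calls for AE tables by closest relationship, and all AEs are listed. This stands in part: the categories could be recovered from those outputs, but the related-event summaries in SAP 7.1 would still be uninformative.

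**Conclusion.** Both rules are wrong as written and should be corrected before database lock.

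The partial-date exception contradicts the TEAE definition in its own section, Protocol 11.2.1 and SAP Appendix 2. Because it feeds the primary endpoint, it must be fixed even though its effect may prove small. The per-subject scale is 6.25 points with 16 per arm, or 5.0 to 5.6 points with 18 to 20 dosed per arm. It applies only to a subject whose TEAE status rests on a misclassified event. It is not an estimate of the total error, because the number of partial-date AEs is not given.

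The relatedness definition contradicts Protocol 10.1.2 and the SAP's own two-level table. Its effect is certain if applied literally: 100% of AEs and SAEs in every arm are related, and the SAP's related-event summaries do not distinguish drug-attributed events from others. It does not change the primary endpoint.

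**What to change.** 1. **Partial dates (SAP 7.1).** Reword the exception so that the TEAE assumption is lifted only when the known parts of the start date, or the end date, show that the event began before the first dose and it did not increase in severity afterwards. State that Appendix 2 imputation is applied first and that the 7.1 default covers only events still undetermined, so that the two sections agree.
2. **Relatedness (SAP 7.1).** Define treatment-related as probable or possible, keep the rule that a missing relationship counts as related, and class the remaining assessments as not related. Align the category list with Protocol 10.1.2 and the CRF: the protocol lists probable, possible and unlikely, with no separate unrelated category.

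The cost is two sentences in SAP 7.1, including the precedence statement, and an update to the AE derivation program. No new data are needed.
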